Aim 2: To measure the effectiveness of the program among participants by evaluating the change in number of individuals reaching two or more of cardiometabolic risk goals, namely reductions in blood pressure, triglycerides, and HbA_{1c} (the primary outcome), and through changes in secondary outcomes including rates of diabetes incidence and regression to normoglycemia and changes in anthropometry, lipids, and fasting glucose.

Aim 3: To measure the value and return on investment of the intervention for employers by assessing program cost and cost-effectiveness and changes in staff productivity, absenteeism, health status, and quality of life.

If the program is shown to be feasible, acceptable, effective, and cost-effective at these worksites, the results of this study will be used to make recommendations and dissemination plans on how to implement and sustain lifestyle interventions at worksites to improve the health of workers and communities for other sites within these companies, other Indian worksites, organizations involved in promoting worksite wellness and/or chronic disease prevention, and to India's National Programme for Prevention and Control of Diabetes, Cardiovascular Diseases, and Stroke. Furthermore, lessons from this study can be used to make recommendations or plan studies of similar worksite programs in the U.S. and other settings outside of India.

Significance

The Diabetes Epidemic: Type 2 diabetes mellitus (T2DM) is an economically costly disease and a major cause of morbidity and mortality globally.^{4,42} Eighty percent of the 382 million people worldwide with diabetes live in low- and middle-income countries.¹ Asian Indians living worldwide are particularly susceptible to developing T2DM, with high prevalences of T2DM and T2DM risk factors (e.g., beta-cell dysfunction, central adiposity), higher rates of progression from prediabetes to diabetes,⁴³ and lifestyles that pre-dispose to T2DM (e.g., high-fat, low fiber diets and low physical activity).^{2,44-46} Asian Indians fare worse than several other populations after developing T2DM (poor glycemic control, higher rates of complications).⁴⁷⁻⁵⁰

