The program evaluation will use mixed methods techniques to assess program acceptability, impact, and effectiveness. Although the goal of the program is to benefit employees, the program evaluation includes measures such as cost-effectiveness, changes in employee absenteeism/presenteeism and qualitative assessments of employee views of the program that will be beneficial to employers using or considering this program for their worksite. In addition, the acceptability and impact of the program will be measured from the perspective of multiple stakeholders – program users, employees at the worksite, and worksite management. Understanding the program outcomes and acceptability from these multiple perspectives will provide rich data for making recommendations for sustaining and disseminating the program.

Although this study will be conducted in India, the results will be applicable to workers in other settings, including the U.S. (see Foreign Justification). Asians, including Asian Indians, are the fastest growing ethnic group in the U.S., and between 2000 and 2010 the Asian Indian population increased by 67.6%.⁷¹ Furthermore, several of the companies committed to this trial (the TATA group, L&T, and Cognizant) have locations worldwide, including offices in America, and these sites would be ideal locations for first phase dissemination. In addition, lessons learned in this study would benefit U.S. companies with worksites in India.

Approach

This study will use a pre-post design at eight diverse worksites to assess program implementation, fidelity, effectiveness, and impact on study participants, workers, and the worksite. There will be no control group because there is already convincing evidence from randomized trials^{8,9,17,53,58,72} that lifestyle intervention is beneficial for preventing diabetes and diabetes-related complications. Although randomized controlled trials provide the most robust evidence for effectiveness, meta-analyses have shown that the results of non-randomized, effectiveness studies do not systematically differ from the results given by randomized controlled trials of the same treatment.^{73,74}

Intervention

The lifestyle intervention will be conducted at eight worksites (see Table 1). These worksites have large workforces (1,500-50,000 employees) and represent a range of industries with locations across India. An overview of activities to be conducted at each worksite are shown in Figure 1.

[figure not shown]

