Quantitative data collection (Table 4) will occur at study-testing visits at baseline and every twelve months after lifestyle classes begin. Whenever possible, validated study instruments will be used. The primary outcome assessing program effectiveness (Aim 2) will be a composite of achieving two or more cardiometabolic risk goals; participants will be scored on the number of risk factors they improve on (0-3) with success delineated by a HbA_{1c} decrease $\geq 0.5\%$; a systolic blood pressure decrease ≥ 5 mm Hg; and a decrease in plasma triglycerides ≥ 10 mg/dl. This outcome was selected for three reasons: other risk scores for CVD (e.g., the Framingham Risk Score) do not perform as well in South Asian populations;⁹³ these risk factors are commonly measured by clinicians, so the results are clinically appropriate; and the composite outcome allows for individual variation in risk factor profiles and the ability of individuals to reduce different factors (e.g., an individual with a baseline HbA_{1c} of 5.8% is unlikely to reduce this risk factor by 0.5%, but may succeed in reducing triglycerides or blood pressure).

Table 4: Quantitative Data Collection Tools

Variable of interest (test)	Outcome of test	Timing			
		S	B	A	FU
Demographics and Lifestyle Behaviors					
Demographics (SQ)	Describe study population	X	X		
History of smoking (SQ)	Smoking status and cessation rates		X	X	X
Global Physical Activity Questionnaire (GPAQ) ⁹⁴	Baseline and changes in physical activity		X	X	X
Dietary intake (food frequency questionnaire)	Study specific food frequency questionnaire on dietary intake of foods targeted in the intervention		X	X	X
Dietary behaviors (SQ)	Prevalence of diet-related behaviors (e.g., reading nutrition		X	X	X

Variable of interest (test)	Outcome of test	Timing			
		S	B	A	FU
Weight loss history (SQ)	labels, eating at restaurants, measuring portions, etc.) Weight loss history including number and success of past attempts, methods used, etc.		X		
Quality of life (EQ-5D)	Baseline and changes in quality of life		X	X	X
Self-reported health (SF-12 and SQ)	Health status, recent health events and medication use (type and dosage of all prescription and over the counter medications and herbal remedies)		X	X	X
Worker satisfaction (SQ)	Questions assessing worker satisfaction with worksite, number of days missed work, self-described levels of productivity		X	X	X
Health-related outcomes					

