ROI (cost-benefit and cost-utility analyses): To estimate potential ROI for worksite leaders, we will calculate an overall cost-benefit in monetary terms. To do this, we will identify the costs incurred by employers in the years prior to the study and costs during the study (incremental investments). We will then identify total benefits (cumulative indirect costs) prior to the study and during the study (annually, and at completion). We will consider: 1. Cost-benefit (ratio of incremental costs to change in productivity) without any health expenditures (assumes employer doesn't pay for employees' health care); 2. Cost-benefit that includes aggregated medical (physician consultations, medications, diagnostic tests, inpatient stays) and lost productivity costs, which assumes employers pay for employee healthcare; and 3. Cost-utility ratio (net costs to net utility: costs of intervention – average costs in previous years / utility of intervention – utility of control). To calculate utility, we will use the 12-monthly health utility measure, the quality adjusted life year (QALY), which is calculated as the sum of mean survival time [life years] x utility scores at 12, 24, and 36 months. We will report 12-, 24-, and 36-month costs per QALY.¹⁰⁸ If the intervention is successful, we will also compare modeled long-term cost-utility of the intervention and usual care using Markov Chain Monte Carlo estimation techniques, controlling for age, gender, and risk factor prevalence under different plausible scenarios for how these may evolve over time.¹⁰⁹ We will compare this to reference points from the literature – e.g., ceiling ratios for costs per QALY that are less than three times GDP per capita¹¹⁰⁻¹¹² are considered cost-effective (India's 2013 GDP per capita was \$3,990; threshold: ≤\$11,100 per QALY).¹¹³ We will use sensitivity analyses to examine the effects of varying discount rates, costs of the intervention, and effectiveness. Drs. [name] and [name] have expertise in economic analysis¹¹⁴⁻¹²³ and will consult with [name], health economist at CDC, as needed.

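### Aim 3 economics: the $11,100 per QALY threshold is not three times the stated GDP per capita of $3,990, and the within-trial cost-utility ratio subtracts a control utility that a trial without a control group does not supply

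*Combined protocol and SAP*

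**What the plan says.** All of the economic text is in the ROI paragraph under Data Analysis, Aim 3, of the combined protocol and SAP.

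- **Threshold.** The paragraph treats ratios below three times GDP per capita as cost-effective, gives India's 2013 GDP per capita as $3,990, and states a threshold of at most $11,100 per QALY. Reference 113, cited at that point, is dated 2012 and was accessed on June 10, 2012.
- **Ratio.** The cost-utility ratio is net costs to net utility, spelled out as "costs of intervention – average costs in previous years / utility of intervention – utility of control". QALYs are built from survival time and utility scores at 12, 24 and 36 months, and the plan adds: "We will report 12-, 24-, and 36-month costs per QALY".
- **Design.** The Approach section says: "There will be no control group because there is already convincing evidence from randomized trials".
- **Utility data.** Table 4 (Data Collection) lists the EQ-5D at baseline, annually and at the end of follow-up, with the purpose "Baseline and changes in quality of life".
- **Other comparators.** The ROI paragraph names usual care as comparator only for a long-term model, to be run if the intervention succeeds.
- **Sensitivity analyses.** These cover "varying discount rates, costs of the intervention, and effectiveness".

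**The concern.** The threshold disagrees with the rule and the input printed beside it. An analyst could apply $11,100 or recompute $11,970, and a ratio falling between the two would be classed differently.

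The cost-utility denominator names a quantity that the trial does not observe. The numerator refers to the same employers' earlier years, while the denominator refers to a control. Unless the reference is fixed beforehand, the analyst must settle it at analysis, possibly with the data in view.

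The economic result has a stated use. The Specific Aims make recommendations and dissemination conditional: "If the program is shown to be feasible, acceptable, effective, and cost-effective at these worksites". The two points therefore bear on one of four conditions for dissemination, not on the test of effectiveness.

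**Working it through.** **Threshold**

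Inputs, all from the ROI paragraph: multiplier 3; GDP per capita $3,990; stated threshold $11,100.

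1. Attempt to reproduce the plan's figure: 3 × 3,990 = 11,970. The plan's 11,100 is not reproduced.
2. Gap: 11,970 − 11,100 = 870, and 870 / 11,970 = 7.3%.
3. Rounding of the GDP figure: 3 × 3,985 = 11,955 and 3 × 3,995 = 11,985. Rounding does not explain the gap.
4. Other multipliers: 1, 2 and 2.5 give 3,990, 7,980 and 9,975. The multiplier implied by the two printed figures is 11,100 / 3,990 = 2.78, not 3.
5. One year's discount, at assumed rates: 11,970 / 1.03 = 11,621 and 11,970 / 1.05 = 11,400. Neither gives 11,100.
6. Back-calculation: 11,100 / 3 = 3,700, which is 290 below 3,990. The two printed figures may come from different years or sources, but that is inference. A source accessed in June 2012 cannot, at that access, have supported a figure for 2013.

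**Cost-utility ratio**

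The possible sources for a control utility are these:

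| Candidate | Where | Utility data stated? |
|---|---|---|
| Concurrent control group | Approach | No such group exists |
| Usual care | ROI paragraph, conditional long-term model | None; source of inputs not given |
| D-CLIP controls | Aim 2 analysis; Sample Size Selection | None; used for the 21% benchmark of the binary primary endpoint |
| CARRS study | Sustainability, Dissemination, and Future Plans | None; part of additional analyses needing separate funding |
| Participants' own baseline | Table 4 | Yes, EQ-5D |

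Only the last has documented utility data. It also fits the pre-post design and the backward-looking numerator. The ROI paragraph does not name it, and its QALY definition lists no baseline score.

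The documents give no utility values, so the size of the effect can only be illustrated. **Every input here is assumed:** net cost $300 per person held fixed; everyone survives 36 months; participants' utility is 0.02 above baseline at 12, 24 and 36 months; no discounting; utility without the program moves by s per year from baseline.

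QALY gain = 3 × 0.02 − s × (1 + 2 + 3) = 0.06 − 6s. Ratio = 300 / gain.

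| s per year | Gain (QALY) | Cost per QALY |
|---|---|---|
| −0.01 | 0.12 | $2,500 |
| −0.005 | 0.09 | $3,333 |
| 0 (baseline carried forward) | 0.06 | $5,000 |
| +0.005 | 0.03 | $10,000 |
| +0.01 | 0 | undefined |

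This shows only that the reference can matter. It does not predict this trial's ratio.

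**The case against.** The strongest reply is that the control term is a wording slip. The design is pre-post, costs are compared with earlier years, and baseline EQ-5D is the only utility reference on hand, so a sensible analyst would use it. Much of this stands: there is one workable resolution, and the scope for choosing a comparator after the fact is small. It does not make the written definition computable, and the remedy is to write down the evident reading.

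Second, the sentence introducing the ceiling follows the long-term model, where usual care is the comparator. On the natural reading the ceiling is applied to that modelled ratio. This also stands. The two errors are therefore separate, and the link from the within-trial ratio to the dissemination condition is looser than it first appears. The missing source for usual-care inputs is a different, narrower gap.

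Third, the planned variation of effectiveness and the model's plausible scenarios may absorb some uncertainty about utility without the program. That is partial cover: both are generic, and neither defines the reference.

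A reader might also infer that the cost-benefit ratios lack a comparator. They do not. Control utility does not enter them, and their reference is stated as "costs incurred by employers in the years prior to the study", set against costs and benefits during the study. Nor do the documents say that a single annual average would be subtracted from several years of study costs. They leave the number of years and the scaling open.

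**Conclusion.** Both errors stand, and both are minor.

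- **Threshold.** The printed figure is $870 (7.3%) below what the plan's own rule and input give. If $3,990 is right, ratios from above $11,100 to below $11,970 per QALY would be misclassed as not cost-effective. A reader might infer that the error can only make the criterion too strict. That holds only if either $3,990 or $3,700 is correct. With the source's date in doubt, neither may be, and a true figure below $3,700 would make $11,100 too lenient. The direction is not settled. The figure is also offered as an example reference point.
- **Ratio.** The within-trial cost-utility ratio cannot be computed as defined, because it needs a utility that neither the design nor any section supplies. How far this would move the reported cost per QALY cannot be derived from the documents. D-CLIP changes in weight, BMI or waist give no basis for a factor, since nothing ties them to utility.

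The reach is confined to the Aim 3 economic analysis. The primary endpoint, sample size and power do not depend on either point.

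**What to change.** 1. **Threshold.** Check the GDP per capita figure, its year and its source, and set the threshold to three times the verified figure. If $3,990 stands, the threshold becomes $11,970; if $11,100 stands, the GDP figure becomes $3,700. If neither is confirmed, replace both. Update reference 113 to a source that covers the stated year.
2. **Ratio.** Before analysis, replace the control term with participants' baseline EQ-5D utility carried forward over the same 12, 24 and 36 months. State how many previous years are averaged, and put those costs on the same horizon as the study costs. Label the result a pre-post ratio. Add the assumed course of utility without the program to the planned sensitivity analyses.

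**Cost.** This needs revised wording, one reconciled pair of figures with its reference, and one added sensitivity analysis. No new data are needed, because the EQ-5D is already collected at baseline and annually.

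**Downside.** Carrying baseline forward is an assumption that this trial cannot test. If employees would have improved without the program, it makes the program look more cost-effective than it is, which is why the pre-post label and the sensitivity analysis are needed.

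### The cost-per-QALY ratio is benchmarked with no sign condition and no sampling uncertainty, so a result that loses QALYs can fall under the ceiling

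*Combined protocol and SAP*

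**What the plan says.** The relevant text is in the combined protocol and SAP, Data Analysis, Aim 3, in the paragraph on return on investment (cost-benefit and cost-utility analyses).

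- **Measure.** Cost-utility is one ratio: "costs of intervention – average costs in previous years / utility of intervention – utility of control". On timing: "We will report 12-, 24-, and 36-month costs per QALY".
- **Long-term model.** "If the intervention is successful, we will also compare modeled long-term cost-utility of the intervention and usual care". It is to use Markov Chain Monte Carlo under several scenarios.
- **Benchmark.** The result is set against literature reference points. The only example is "ceiling ratios for costs per QALY that are less than three times GDP per capita", and such ratios count as cost-effective. The same sentence gives GDP per capita as $3,990 and the limit as "11,100 per QALY".
- **Uncertainty.** "We will use sensitivity analyses to examine the effects of varying discount rates, costs of the intervention, and effectiveness".
- **Employer return.** One measure is "Cost-benefit (ratio of incremental costs to change in productivity"), leaving health spending out; a second version adds medical costs. Neither has a ceiling.

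The paragraph has no requirement that net utility be positive, no treatment of dominated results, and no interval or probability of cost-effectiveness. The Approach section says the study has no control group, yet the ratio subtracts a control utility.

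**The concern.** A cost-per-QALY ratio can be read against a ceiling only when its denominator is positive. Once the estimated QALY change is negative, the comparison runs the wrong way. Near zero, the ratio is unstable in both size and sign.

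A QALY change near zero is realistic here. The ratio is reported as early as 12 months, and the introduction to Aim 3 promises per-site as well as cumulative estimates. If participants' own baseline stands in for the missing control, ageing alone could lower utility.

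The closing paragraph of the Specific Aims makes cost-effectiveness one of four conditions for recommending the programme to other worksites and to India's national programme. The sustainability section relies on the same finding to appeal to management. Aim 2 specifies clustering, interval estimates and p-values for effectiveness; the Aim 3 ratio has none of these.

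**Working it through.** **1. The plan's own threshold.** Inputs: GDP per capita $3,990 and a multiplier of three, both from the benchmark sentence.

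3 x 3,990 = 11,970, against a stated 11,100. The shortfall is (11,970 - 11,100) / 11,970 = 7.3%. Working backwards, 11,100 / 3 = 3,700 and 11,100 / 3,990 = 2.78. The stated figure is not reproduced.

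**2. Sign of the ratio.** Let dC be net cost, dQ the QALY change and L the ceiling. Net monetary benefit is NMB = L x dQ - dC.

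- If dQ > 0, then dC/dQ < L is the same statement as NMB > 0.
- If dQ < 0, multiplying through by dQ reverses the inequality, so dC/dQ < L is the same statement as NMB < 0.

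For any QALY loss, the ratio therefore meets the ceiling exactly when the programme is poor value at that ceiling. Illustrative values at L = $11,100:

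| dC | dQ | Ratio | Under ceiling? | NMB |
|---|---|---|---|---|
| +$100 | -0.01 | -$10,000 | yes | -111 - 100 = -$211 |
| -$100 | -0.02 | +$5,000 | yes | -222 + 100 = -$122 |
| -$200 | -0.01 | +$20,000 | no | -111 + 200 = +$89 |

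The first row costs money and loses health. The second saves too little for the health lost. The third would be acceptable at the ceiling but fails. At $11,970 the NMBs are -$219.70, -$139.40 and +$80.30, so no row changes.

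**3. Sampling error, under assumptions.** Sample Size Selection gives 8 sites x 250 = 2,000 enrolled and, after 20% loss, 1,600 (200 per site). The documents give no SD of QALYs, ICC or net cost. Assumed ranges: SD of the 3-year QALY difference 0.15 to 0.6, ICC 0 to 0.05, net cost $50 to $400 per participant with cost SD half the mean.

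Middle case (SD 0.3, ICC 0.01, net cost $200):

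- Design effect = 1 + 199 x 0.01 = 2.99.
- SE(dQ) = 0.3 x sqrt(2.99 / 1,600) = 0.013.
- Break-even dQ = 200 / 11,100 = 0.018.
- SE(NMB) is about 11,100 x 0.013 = $144; the cost SD adds almost nothing.
- If true dQ = 0, the estimate is negative with probability 0.50. It is positive with NMB > 0 with probability P(Z > 200/144 = 1.39) = 0.08.

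The chance of falling under the ceiling on a literal reading of point estimates is then 0.50 + 0.08 = 58% (60% at $11,970). Of this, 50 points come only from counting negative ratios as favourable. Requiring NMB > 0 gives 8%, and requiring its lower 95% bound to exceed zero gives less than 0.1%.

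Over the assumed ranges with true dQ = 0, the three figures are 50-96%, 0-46% and at most 2.0%. At true break-even, the lower-bound rule gives 2.5%.

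For one site, SE(dQ) = 0.3 / sqrt(200) = 0.021, which exceeds the 0.018 break-even. Under the middle assumptions, the sign at single sites would be unreliable.

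**The case against.** The strongest reply is that this is not a decision rule. The ceiling is an example of a literature benchmark, and no sentence says a ratio below it will settle the matter. Aim 3 is meant to inform stakeholders about costs and returns. In sentence order, the benchmark attaches most directly to the long-term model, which runs only if the intervention succeeds; that makes a QALY loss less likely to reach it. Costs, productivity and health status are also analysed separately, and EQ-5D is collected, so a loss of health would not be hidden.

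Much of this stands, and it rules out several stronger readings that a reader might infer:

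- *That the plan would accept a harmful programme.* It never says so. It only omits the condition that would prevent it.
- *That the benchmark is applied to bare point estimates.* The text is silent on this.
- *That sensitivity analyses are one-at-a-time, or are the only treatment of uncertainty.* Neither is stated, and the MCMC scenarios are also planned.
- *That the productivity ratio fails in the same way.* It has no ceiling, so nothing is accepted or rejected. A negative denominator there makes the ratio hard to interpret, no more.
- *That false acceptance occurs at least half the time.* This needs a true QALY change of zero, positive net cost, and analysts who read a negative ratio as favourable.

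The gap remains. This is the only cost-per-QALY criterion the plan states. Success is undefined, and the primary endpoint is a risk-factor composite, so the condition on the model does not exclude a negative QALY change. Varying inputs or running scenarios is not an interval, and neither is linked to the benchmark.

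**Conclusion.** The concern holds as a gap in specification, of moderate weight. The sign result is exact and needs no assumption: whenever the QALY change is negative, comparing the ratio with the ceiling gives the reverse of the net-benefit answer. The missing link between sampling or worksite-level uncertainty and the benchmark is plain from the text. The threshold discrepancy ($11,970 against $11,100, or 7.3%) is firm arithmetic, though it does not drive the sign problem.

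The probabilities above rest on assumed SD, ICC and net cost and are illustrations, not predictions. No primary or secondary effectiveness result is affected; only the Aim 3 economic conclusion is.

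**What to change.** 1. Make net monetary benefit at the stated ceiling (ceiling x QALY change minus net cost) the main cost-utility summary at each time point.
2. Give it a 95% interval that includes between-worksite variation, by resampling worksites. Check it with a t-interval on the eight site means (7 degrees of freedom). Resampling participants within fixed sites is not enough: it omits variation between sites, and some programme costs are recorded per campus, so they have only eight values.
3. Add an acceptability curve over a range of ceilings.
4. Report dominated or QALY-losing results as such. Show the ratio only when net cost and QALY change are both positive.
5. Report the employer analysis as net benefit in money with an interval. This is for interpretability, since no ceiling applies there.
6. Correct the threshold: three times the plan's own $3,990 is $11,970. If $11,100 was intended, the GDP figure must change instead.
7. Name the source of the control utility. The QALY change cannot be computed without it.

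The cost is SAP wording and a little more analysis of data the plan already collects. The conclusion may be less favourable.
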